3.3.2 PK SAMPLING

A total of 180 children will undergo intensive PK sampling. Of these 180, 60 will be main trial children (in PediCAP-A) who were randomised to oral co-amoxiclav 7:1 step-down (see [Section 10.1.1](#)). These should be children randomised to co-amoxiclav in the main trial; however, additional consent will be sought for this, which may be refused and children still join the main trial. In total 60 of the 500 children randomised to co-amoxiclav 7:1 in PediCAP-A will undergo PK sampling.

An additional, but separate, 120 children meeting the same eligibility criteria above will undergo randomisation to two different co-amoxiclav formulation strengths, 4:1 vs 14:1, and undergo intensive PK sampling in a parallel Phase II PK trial (PediCAP-B) (see [Section 10.1.2](#)). These children will receive 6 days total antibiotics (the median in the main trial). This randomisation will not be stratified by site, but will be stratified by weight-band. All other investigations and follow-up will be identical.

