6.2 CHILDREN UNDERGOING PK SAMPLING

A total of 180 children will undergo PK sampling. This will consist of 60 children in the main trial (PediCAP-A) randomised to co-amoxiclav and receiving the standard co-amoxiclav 7:1 ratio (independently of total duration of antibiotic therapy randomisation). A further 120 children will be randomised to oral step-down with co-amoxiclav 4:1 versus 14:1 ratios (60 in each group) in a Phase II PK trial (PediCAP-B). The assessment schedule for these 120 additional children will be the same as for children in the main trial. For all patients undergoing PK sampling, additional informed consent will be sought for taking PK samples. Children will have up to 5 PK samples taken immediately before and then over up to 12h after their first morning dose. See [Section 10.1](#) for more details.

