6.7 PROCEDURES FOR ASSESSING SAFETY

The clinical examination at each face-to-face contact and follow-up telephone calls will explicitly prompt for symptoms relating to possible drug toxicities. Additional safety blood tests or investigations may be performed to investigate symptoms or monitor emergent laboratory test abnormalities as clinically indicated following routine clinical practice. Results of any laboratory tests conducted as part of routine clinical practice will be recorded on CRFs\worksheets.

Adverse events (clinical and laboratory) will be graded using the 2017 Division of AIDS (DAIDS) toxicity grading scale v2.1 (see [Appendix I](#)), with a minor modification of the neutrophil count grading to reflect norms in the African populations. All adverse events of any grade that lead to modification of antibiotics or are considered related to antibiotics will be reported on CRFs\worksheets, as will any Grade 3 or 4 adverse events and SAEs. Other adverse events will be recorded in the clinical notes but will not be reported on CRFs\worksheets – the reason is that grade 1 and 2 adverse events will be very common as the children will be sick when admitted. They will therefore not be informative as they commonly reflect the underlying disease process rather than any impact of the medication. SAEs (and other notable events) will be defined according to ICH GCP, and should be reported to the CTU within 1 working day of the site being aware (see [Section 7](#)). All adverse events meeting these SAE definitions should be reported on study CRFs\worksheets, regardless of their relationship to pneumonia.

Telephone follow-up calls will explicitly prompt for known clinical adverse effects of amoxicillin and co-amoxiclav, primarily gastrointestinal symptoms including diarrhoea, vomiting, rash and thrush/candida. Additional investigations may be performed to investigate symptoms or monitor emergent laboratory test abnormalities as clinically indicated.

Pre-specified clinical complications including sepsis, lung abscess, empyema, and line complications will be recorded on the CRF\worksheet.

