9.2.2 SECONDARY OUTCOME MEASURES

Efficacy/effectiveness secondary outcomes (assessed in all children) are:

- Proportion of children experiencing CAP-related readmission to hospital or CAP-related death within 28 days post-randomisation (CAP-relatedness adjudicated by the independent Endpoint Review Committee)
- Length of stay required during the index hospitalisation (days) (excluding any additional day remaining in hospital solely for the purpose of trial-related pharmacokinetic studies, see [Section 10.1](#)), and total days of stay in hospital up to 28 days
- Proportion of children dying within 28 days post-randomisation (all-cause mortality)
- Total days of supplemental oxygen during index hospitalisation
- Total days of antibiotic exposure during 28 days post-randomisation, including antibiotics received during the initial hospitalisation and antibiotics self-reported by parents/carers at follow-up visits
- Proportion of children requiring modification of randomised antibiotics for any reason other than early stopping, or requiring a subsequent course of antibiotics for any reason up to 28 days (also considered as separate components)
- Proportion of children requiring modification of randomised antibiotics for inadequate response, or additional courses in the index hospitalisation for CAP relapse

Safety secondary outcomes (assessed in all children) are the proportion of children:

- Experiencing SAEs, including hospital-acquired infections

- Experiencing grade 3 or 4 adverse events
- Experiencing antibiotic-related adverse events
- Experiencing key solicited events (reflecting common drug toxicities), specifically diarrhoea, vomiting and gastrointestinal disorders, skin rashes, thrush/candida
- Modifying antibiotics for antibiotic-related adverse events (i.e. toxicity)
- Experiencing specified clinical complications including sepsis, lung abscess, empyema
- Experiencing line complications (complications related to IV access)

Note that by definition a hospital-acquired infection prolongs hospitalisation so is an SAE following [Section 7](#). Therefore, the SAE secondary endpoint will include all hospital-acquired infections.

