10.1.1 PHARMACOKINETIC SAMPLING IN CHILDREN RANDOMISED IN THE MAIN TRIAL (PEDI CAP-A)

A subset of children joining the main trial (PediCAP-A) will be approached for additional written informed consent to take part in a PK substudy of the 7:1 co-amoxiclav formulation if they are randomised to oral co-amoxiclav step-down. In total, 60 children with a complete set of PK samples (defined below) will be included (out of the total 500 randomised to 7:1 co-amoxiclav in PediCAP-A), targeting a minimum of 6 children per weight-band from 6kg up to 25kg to ensure a minimum dataset is generated for each proposed dose in the main weight range.

PK sampling will occur immediately before and then after the first morning dose and will consist of 5 samples per child weighing 6kg or more (2ml per sample); e.g. before observed dosing (5-10 min pre-dose), during early absorption (0.25-1h post dose), around the expected C_{max} (1-2h), during early disposition (2-6h), and in the terminal phase (6-12h). Optimal design and model-based stochastic simulation-estimation will be used to determine the exact sampling windows (which will maximise the information obtained from sampling compared to fixed sampling times) and the allocation of children between the weight-bands, while keeping the total pre-specified sample size. Allowable blood draws are 10ml or more in unwell children weighing 5kg or more ([Appendix II](#)): any child weighing less than 5kg will have one (4kg) or two (3kg) of the 5 PK samples dropped (chosen according to the optimal design) and will be considered to have a complete PK sample set (leading to total blood draws over 12h of 8ml and 6ml respectively). A cannula will be used to avoid repeated venepuncture, and anaesthetic cream to numb the child's skin.

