Any child consenting to the PK substudy who does not have the complete set of PK samples taken for any reason (e.g. refusal of later samples) will be replaced, to give a total of 60 children with a complete set of PK samples. PK data from samples from any children not providing the full set will nonetheless be pooled for the model-based analysis (see below). For some children, this may require a short period of additional hospitalisation (e.g. if they would otherwise have been discharged mid-morning, but need to stay until the evening for the final PK sample), which will be clearly explained to each parent/carer, has been costed as part of the trial, and will not contribute to the trial secondary endpoint, length-of-stay. Parents/carers will be given travel money for the extra PK day.

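### Complications of the PK cannula could be counted against co-amoxiclav only, because the line-complication outcome has no PK exclusion like the one for length of stay

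*Protocol*

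**What the plan says.** Section 9.2.2 introduces the safety outcomes with "Safety secondary outcomes (assessed in all children) are the proportion of children" and includes "Experiencing line complications (complications related to IV access". Nothing limits this to lines used for treatment. Section 6.7 adds only that "empyema, and line complications will be recorded on the CRF", with no field for which line was involved.

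PK sampling in the main trial is confined to one drug. Section 3.3.2 states that "60 of the 500 children randomised to co-amoxiclav 7:1 in PediCAP-A will undergo PK sampling", and 6.2 describes the sampled group as "60 children in the main trial (PediCAP-A) randomised to co-amoxiclav and receiving the standard co-amoxiclav 7:1 ratio". No child on amoxicillin and none in the continuous intravenous group is sampled.

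Section 10.1.1 says "A cannula will be used to avoid repeated venepuncture". The sampling runs from just before the first morning oral dose to as late as 12h after it. Sections 10.1.1 and 11.2.1 also mention anaesthetic cream. Children with incomplete sets are replaced until 60 complete sets are obtained.

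For one other outcome the protocol deals with the effect of PK sampling. Section 9.2.2 excludes from index length of stay any extra day spent in hospital only for PK, and 10.1.1 repeats that the added stay "will not contribute to the trial secondary endpoint, length-of-stay".

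**The concern.** A complication of the PK cannula meets the definition in 9.2.2 as written, and in PediCAP-A it can occur in only one arm of the randomised drug comparison. Any such event adds to the co-amoxiclav proportion for a reason that has nothing to do with the drug. The same events would count against co-amoxiclav step-down when it is compared with five days of intravenous treatment, and 11.2.1 names fewer line complications as a possible benefit of step-down.

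The protocol recognised that PK procedures distort length of stay and corrected this in the outcome definition. Line complications are exposed to the same procedure without that protection. The Endpoint Review Committee (9.2.4 and 14.5) is described mainly in terms of deaths, readmissions and CAP-relatedness, so no stated step would filter these events out. If the source of a complication is not recorded when it happens, it cannot be recovered reliably at analysis.

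**Working it through.** **Inputs from the protocol.** PK-sampled children in PediCAP-A: 60 complete sets (3.3.2, 6.2, 10.1.1). Children randomised to co-amoxiclav 7:1: 500 (3.3.2). PK-sampled children on amoxicillin: 0. The protocol states no figure for line complications, so there is none to reproduce.

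**Assumed inputs.** Let *c* be the risk that the PK cannula, or the extra time an existing line stays in for PK, causes a complication. Let *b* be the background risk of a treatment-line complication. The protocol gives neither.

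**Step 1, exposure.** 60/500 = 12% of the co-amoxiclav arm, against 0/500 = 0% of the amoxicillin arm. Over both oral arms together it is 60/1,000 = 6%.

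**Step 2, shift in the co-amoxiclav proportion.** Shift ≈ 0.12 × *c*; extra children ≈ 60 × *c*.

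| Assumed *c* | Extra children | Shift (percentage points) |
|---|---|---|
| 2% | 1.2 | 0.24 |
| 5% | 3 | 0.6 |
| 10% | 6 | 1.2 |

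Because incomplete sets are replaced, more than 60 children may be cannulated. With 70 (an assumption), exposure is 70/500 = 14% and the shift is 0.14 × *c*, or 0.28 to 1.4 points over the same range.

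**Step 3, allowing for children already counted.** The outcome is a proportion of children, so a child with a treatment-line complication is not counted twice. If the two risks are independent, the shift becomes 0.12 × *c* × (1 − *b*). Suppose also that the PK cannula is exactly as risky as the treatment line (*c* = *b*), and compare the shift with the standard error of a difference between two arms of 500, √(2*b*(1 − *b*)/500):

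| *b* = *c* | Shift (points) | SE (points) | Shift/SE |
|---|---|---|---|
| 2% | 0.12 × 0.02 × 0.98 = 0.24 | 0.89 | 0.27 |
| 5% | 0.12 × 0.05 × 0.95 = 0.57 | 1.38 | 0.41 |
| 10% | 0.12 × 0.10 × 0.90 = 1.08 | 1.90 | 0.57 |

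**Step 4, effect on a nominal two-sided 5% test with no true drug effect.** The chance of a significant result is approximately P(Z > 1.96 − d) + P(Z < −1.96 − d), with d the last column. This gives about 6%, 7% and 9% instead of 5%.

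**Step 5, primary outcome.** Readmission or death does not use the line-complication item. The stated power of over 80% reproduces at 81.3% (15% versus 9%, 475 per arm after 5% loss) and is untouched.

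**The case against.** The strongest objection is that this is detail for the SAP, CRF or manual of operations. Section 9.5 defers analysis detail to the SAP, and those documents are not shown. That holds for the form of any sensitivity analysis. It does not dispose of the point, because the outcome definition is set in the protocol, the length-of-stay exclusion was placed there, and a SAP cannot separate events whose source was never recorded.

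A second objection concerns the mechanism, and it stands in part. Every child has at least 24h of intravenous treatment (5.2.1), and 10.1.1 does not say whether the PK cannula is a new line or the existing one. A reader might infer that a new research line is always inserted and that its complications are certain to be charged to co-amoxiclav. The anaesthetic cream suggests new insertions but does not settle it. Reuse would still keep a line in for PK in co-amoxiclav children only, with a smaller added risk. The outcome wording could also be read as covering only access for intravenous therapy, but the protocol does not say so.

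A third objection is that the effect is small and its size assumed. This stands. A reader might infer a serious risk of a false safety signal. With *b* = 2% and *c* = 20% the chance of a nominally significant excess on co-amoxiclav would be about 56%, but that makes a cannula used for up to 12h ten times as risky as treatment lines used for at least 24h, and nothing in the protocol supports it.

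Finally, the protocol's stated interest in line complications (11.2.1) is step-down against intravenous treatment, where the shift runs against step-down and is conservative for a claimed benefit. That lessens the consequence there. It does not help the comparison of the two oral drugs.

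**Conclusion.** The point holds as a minor one. The one-sided exposure (at least 12% against 0%) and the missing exclusion are both in the text, so complications of a line placed or kept for PK could be counted against co-amoxiclav only. Whether they will be, and how many, cannot be determined from the protocol. The shift is 0.24 to 1.2 percentage points for an assumed *c* of 2% to 10%, and less with line reuse or an earlier treatment-line complication. If the PK cannula is no riskier than a treatment line, the shift is roughly 0.3 to 0.6 of a standard error. It concerns one secondary safety outcome. The documents do not support any inference that the primary outcome, its power or the non-inferiority comparison is affected. PediCAP-B is also outside the problem, since all 120 children there are sampled in both groups.

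**What to change.** - **Definition (9.2.2).** Exclude from the between-arm comparison complications arising solely from a cannula placed or kept for PK sampling, to match the length-of-stay exclusion.
- **Recording (CRF).** Add a source item to the line-complication entry: treatment line, PK cannula, or both/unclear. Count both/unclear as treatment line.
- **Reporting.** Show PK-line complications separately so that no safety event is lost. Because attribution is made open-label, also report the result for all lines.
- **Sensitivity analysis, if one is wanted.** Drop PK consenters from all randomised groups. The note to the trial schema says PK consent is sought before randomisation, so that subset is comparable across groups provided consent status is held for every group. Dropping only the PK-sampled co-amoxiclav children would remove a selected set from one arm and break the randomised comparison.

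The cost is one sentence, one CRF item and a few reporting lines. The downside is an attribution rule applied by unblinded staff, and it works only for complications recorded after the item is added.

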1.4.1 RATIONALE FOR DESIGN OF ORAL-STEP DOWN COMPARISONS

First, rapid step-down to oral antibiotics would enable earlier discharge from hospital and reduce risks of nosocomial infections/acquisition of resistant bacteria. While step-down treatment with **oral amoxicillin** may be effective, **oral co-amoxiclav**, a combination of amoxicillin and the beta-lactamase inhibitor clavulanate, is an alternative that will also treat MSSA and respiratory Gram-negative bacteria, maintaining the advantage of the broader spectrum offered by the intravenous regimens. This is particularly pertinent considering the current global and African context of increasing antimicrobial resistance. An advantage of using co-amoxiclav is that dosing regimens can closely follow those of amoxicillin, while a disadvantage could be a higher rate of antibiotic-associated diarrhoea [31]. Within the main trial (PediCAP-A), this question regarding relative benefits and risks of step-down with oral amoxicillin vs co-amoxiclav will be made by using a standard 1:1 randomisation, and comparison with the hypothesis that oral co-amoxiclav will be superior to oral amoxicillin.

However, different ratios of the two component drugs in co-amoxiclav are used worldwide and there are no data to support which might be optimal. For the main comparison above, we will use the 7:1 amoxicillin:clavulanate ratio which is the European Medicines Agency (EMA) approved ratio for twice daily dosing of co-amoxiclav in children, and is most widely used worldwide. However, the 14:1 ratio might achieve broadly similar clavulanate levels with fewer side-effects whereas the 4:1 ratio formulation might achieve greater clavulanate levels and potentially greater efficacy. In a parallel Phase II pharmacokinetic trial (PediCAP-B), we will therefore evaluate the drug concentrations of amoxicillin and clavulanate achieved when 4:1, 7:1, and 14:1 ratios of co-amoxiclav are used twice-daily in children with severe pneumonia. Rates of antibiotic-associated adverse events will also be compared between these groups.

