5.2 INTRAVENOUS ANTIBIOTICS (ALL CHILDREN)

5.2.1 PRODUCTS & TREATMENT SCHEDULE

At the point of randomisation, children should have received no more than 24h of intravenous antibiotics ([Section 3](#)). However, standard-of-care intravenous treatment should be for at least 24 hours for all children, whether randomised to oral step-down or continuous intravenous antibiotics and regardless of what duration of intravenous antibiotics has been received at the point of randomisation. That is, children randomised to step-down to oral antibiotics should not do so before receiving at least 24h of intravenous antibiotics. Those randomised to intravenous antibiotics will be treated with intravenous antibiotics for 5 days in total (from start of intravenous antibiotics, excluding oral/intramuscular antibiotics received in the community). Parents/carers of children randomised to 5 days' IV will receive travel costs for any additional days their child remains in

hospital solely for the purpose of receiving intravenous antibiotics within the trial, since a few of these children might otherwise be discharged early on oral antibiotics depending on local practice (site-specific).

Dosing should follow the local standards of care (summarised in [Table 6](#)) which generally follow WHO recommendations where given ([Table 2](#)). Local standards of care may differ from WHO recommendations due to factors such as local susceptibility patterns, drug availability and institutional prescribing guidelines.

The choice of intravenous antibiotics will be made by the treating physician prior to randomisation. Doses should be given intravenously: if there is a problem with venous access, then isolated post-randomisation doses that should have been given intravenously may be given intramuscularly. Doses will be dispensed from ward stock and prepared and given by the ward nurses. Children will be hospitalised for the entire parenterally administered treatment duration (5 days for those randomised to intravenous antibiotics). After completing their intravenous antibiotics (either after 5 days or after moving to oral-stepdown), children should be discharged as soon as they are clinically stable.

Table 6: Dosing of standard intravenous antibiotics

DRUG	SCHEDULE
Ampicillin	IV/IM: 50 mg/kg every 6 hours
Benzylpenicillin (penicillin G)	IV: 50'000-100'000 U/kg every 6 hours
Cefotaxime	IV: 50 mg/kg every 6 hours or 33.3 mg/kg every 8 hours

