7.1 DEFINITIONS

The definitions of the EU Directive 2001/20/EC Article 2 based on the principles of GCP apply to this trial protocol. These definitions are given in [Table 9](#).

Table 9: Adverse events definitions

TERM	DEFINITION
Adverse Event (AE)	Any untoward medical occurrence in a patient or clinical trial subject to whom a medicinal product has been administered, including occurrences that are not necessarily caused by or related to that product.
Adverse Reaction (AR)	Any untoward and unintended response to an investigational medicinal product related to any dose administered.
Unexpected Adverse Reaction (UAR)	An adverse reaction, the nature or severity of which is not consistent with the information about the medicinal product in question, as set out in the Summary of Product Characteristics (SPC) or Investigator Brochure (IB) for that product.
Serious Adverse Event (SAE) or Serious Adverse Reaction (SAR) or Suspected Unexpected Serious Adverse Reaction (SUSAR)	Any adverse event, adverse reaction or unexpected adverse reaction that: 
 ▪ Results in death ▪ Is life-threatening* ▪ Requires hospitalisation or prolongation of existing hospitalisation** ▪ Results in persistent or significant disability or incapacity ▪ Consists of a congenital anomaly or birth defect ▪ Is another important medical condition***

*The term life-threatening in the definition of a serious event refers to an event in which the patient is at risk of death at the time of the event; it does not refer to an event that hypothetically might cause death if it were more severe, for example, a silent myocardial infarction.

**Hospitalisation is defined as an inpatient admission, regardless of length of stay, even if the hospitalisation is a precautionary measure for continued observation. Hospitalisations for a pre-existing condition, that has not worsened or for an elective procedure do not constitute an SAE.

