7.3 INVESTIGATOR RESPONSIBILITIES

7.3.1 INVESTIGATOR ASSESSMENT

7.3.1.A Seriousness

When an AE or AR occurs, the investigator responsible for the care of the child must first assess whether or not the event is serious using the definition given in [Table 9](#). If the event is serious, then an SAE/Other Notable Event Form must be completed and the CTU notified within 1 working day.

7.3.1.B Severity or Grading of Adverse Events

The severity of all AEs and/or ARs (serious and non-serious) in this trial should be graded using the 2017 Division of AIDS (DAIDS) toxicity grading scale v2.1 in [Appendix I](#), with a minor modification of the neutrophil count grading to reflect norms in the African population.

7.3.1.C Causality

The investigator must assess the causality of all serious events or reactions in relation to the trial therapy, as related or unrelated, using the definitions in [Table 10](#). The level of certainty supporting the two categories of related vs unrelated can vary: [Table 10](#) shows how the five categories of the Naranjo classification (unrelated, unlikely, possible, probable, and definitely related to receipt of the study drug) map onto the related/unrelated categories. If the causality assessment is unrelated or unlikely to be related, the event is classified as an unrelated SAE. If the causality is assessed as possible, probable or definitely related, the event is classified as an SAR.

Table 10: Assigning Type of SAE Through Causality

SAE TYPE	FURTHER DETAILS OF RELATIONSHIP	DESCRIPTION
SAR (related)	Definitely	There is clear evidence to suggest a causal relationship and other possible contributing factors can be ruled out.
SAR (related)	Probable	There is evidence to suggest a causal relationship and the influence of other factors is unlikely.
SAR (related)	Possible	There is some evidence to suggest a causal relationship (for example, because the event occurs within a reasonable time after administration of the trial medication). However, the influence of other factors may have contributed to the event (for example, the child's clinical condition, other concomitant treatments).
Unrelated SAE	Unlikely	There is little evidence to suggest that there is a causal relationship (for example, the event did not occur within a reasonable time after administration of the trial medication). There is another reasonable explanation for the event (for example, the child's clinical condition, other concomitant treatment).

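### Section 9.2.2 says the SAE outcome contains every hospital-acquired infection, but the reporting rules in Sections 6.7 and 7 let mild ones that do not prolong stay go uncounted

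*Protocol*

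**What the plan says.** The safety outcomes in Section 9.2.2 include the proportion of children "Experiencing SAEs, including hospital-acquired infections". A note below the list explains why no separate item is needed: "by definition a hospital-acquired infection prolongs hospitalisation so is an SAE following" Section 7. It then concludes: "Therefore, the SAE secondary endpoint will include all hospital-acquired infections".

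Section 7.1 (Table 9) sets out what makes an event serious. The relevant line is "Requires hospitalisation or prolongation of existing hospitalisation". The other criteria are death, threat to life, disability or incapacity, congenital anomaly, and another important medical condition by medical judgement. Hospital-acquired infection is not listed. Under Section 7.3.1.A the responsible investigator "must first assess whether or not the event is serious using the definition given in" Table 9.

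Sections 6.7 and 7.3.1.E decide which non-serious events reach the CRF: grade 3 or 4 events, events related to antibiotics, and events that lead to a change of antibiotics. For the rest, "Other adverse events will be recorded in the clinical notes but will not be reported on" the CRFs or worksheets.

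On length of stay, Section 5.2.1 says "Children will be hospitalised for the entire parenterally administered treatment duration (5 days for those randomised to intravenous antibiotics"). Step-down children are to go home once clinically stable and after keeping down at least one oral dose (criteria for moving to oral antibiotics, Section 5.3.1). Section 1.4.1 gives among the reasons for step-down that it would "reduce risks of nosocomial infections/acquisition of resistant bacteria".

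**The concern.** The outcome section promises a complete count and rests it on a property that the reporting section does not contain. Whether an infection prolonged a stay is a fact about each case. It does not follow from where the infection was acquired. If sites follow Table 9 as instructed, some hospital-acquired infections will be judged non-serious, and some of those will never reach the database.

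Two things are at stake. The first is whether the outcome contains what it is said to contain. The second is comparability. Prolongation is measured against the discharge that would otherwise have happened, and the protocol sets that differently for the IV and step-down groups. Seriousness, and with it capture, may then depend on the allocated arm for a harm that the rationale names as one step-down should reduce. Hospital-acquired infection has no outcome line of its own, whereas line complications do.

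**Working it through.** The protocol states no rate of hospital-acquired infection, no share that prolongs stay, and no power for this outcome, so there is no figure to reproduce. The check is a comparison of text, followed by an illustration of direction.

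**1. The premise against Section 7.**

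| Place | What it does with a hospital-acquired infection |
|---|---|
| 9.2.2, note | Treats each one as prolonging stay, hence as an SAE under Section 7 |
| 7.1, Table 9 | Does not list it; needs actual admission or prolongation, or another criterion |
| 7.3.1.A | Investigator judges each event from Table 9 |
| 7.2 | Notable events are limited to overdose, abuse and misuse |
| 6.7 and 7.3.1.E | If not serious, reported only if grade 3-4, antibiotic-related or leading to antibiotic change |

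Nothing in Section 7 tells a site that every such infection is reportable.

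**2. One case followed through.** Take a mild upper respiratory infection that starts on the ward more than 48 hours after admission and clears before the child would have left anyway.
- Table 9: no death, threat to life, extra stay, disability or anomaly. The important-condition route depends on judgement and is unlikely for a mild illness. Result: not an SAE.
- Sections 6.7 and 7.3.1.E: grade 1-2, unrelated, no antibiotic change. Result: clinical notes only.
- Other outcomes in 9.2.2: not a solicited event (diarrhoea, vomiting or gastrointestinal disorder, rash, thrush), not sepsis, lung abscess or empyema, not a line complication.

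The infection is therefore missing from an outcome said to include all of them.

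**3. Dependence on arm.** An IV child stays for the five days of treatment. An infection that clears within those days prolongs nothing. The same infection in a step-down child about to go home can delay discharge and so become an SAE. In the other direction, a step-down child who leaves early and shows the infection at home meets the hospitalisation criterion only if readmitted, while the IV child is still under daily inpatient observation.

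**4. Direction, by illustration.** All risks and capture fractions here are assumptions; none come from the protocol. Let p be the true risk and c the fraction captured. The observed risk difference (IV minus step-down) is p(IV) × c(IV) − p(SD) × c(SD).

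| True risk IV / step-down | True difference | Capture 50% / 90% | Capture 50% / 50% | Capture 90% / 50% |
|---|---|---|---|---|
| 3% / 2% | 1.0 | 1.5 − 1.8 = −0.3 | 1.5 − 1.0 = 0.5 | 2.7 − 1.0 = 1.7 |
| 5% / 3% | 2.0 | 2.5 − 2.7 = −0.2 | 2.5 − 1.5 = 1.0 | 4.5 − 1.5 = 3.0 |
| 10% / 5% | 5.0 | 5.0 − 4.5 = 0.5 | 5.0 − 2.5 = 2.5 | 9.0 − 2.5 = 6.5 |

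Differences are in percentage points. Lower capture in the IV arm shrinks or reverses the difference, equal capture halves it and leaves the relative risk unchanged, and lower capture in step-down inflates it.

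**5. Sensitivity of the comparison itself.** With 100 IV children against all 1,000 step-down children and full capture, power at two-sided 0.05 is about 14%, 24% and 54% for the three pairs of risks. The comparison would be mainly descriptive in any case.

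**The case against.** The strongest reply is that Section 9.2.2 plainly intends every hospital-acquired infection to count, so the note can be read as deeming each one serious. A Safety Reporting Plan is mentioned in Section 8.1 and may instruct sites accordingly. The intent is clear, and the plan is not available to check. But the note does not present itself as a new rule: it points to Section 7 as its source, and Section 7 is what investigators apply. Nor is hospital-acquired infection defined for reporting. The only onset threshold is in exclusion criterion 2, where it serves eligibility.

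The second reply is that most infections that matter are caught by other routes: grade 3-4 events, sepsis, line complications, any change of antibiotics or later course, and the important-condition criterion. This stands, and it narrows the gap to mild, unrelated, non-solicited infections without antibiotic change. A reader might think that ward gastroenteritis is lost. It is not, because diarrhoea and vomiting are solicited at inpatient assessments and follow-up calls and form their own outcome, although they would not be labelled as hospital-acquired.

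A reader might also infer that the under-count falls mainly on the IV group and hides a benefit of step-down. The documents do not support that. Section 5.2.1 sets five days of inpatient treatment and then discharge when stable, with no compulsory discharge on day 5, so a child still unwell stays and that is prolongation. Infections that surface after an early discharge can be missed in the step-down groups. These effects oppose each other and the protocol gives nothing with which to net them.

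**Conclusion.** The point holds as an inconsistency between the outcome definition and the reporting rules. The premise in Section 9.2.2 has no basis in Section 7, and the claim of complete inclusion is not secured by Table 9 together with Sections 6.7 and 7.3.1.E. The affected events are hospital-acquired infections that are mild, non-solicited, judged unrelated, without antibiotic change, and that do not lengthen the stay.

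Capture may differ by arm because prolongation is judged against an arm-specific stay. Direction and size are undetermined: the table above gives anything from a reversed to an inflated difference, depending on capture fractions that are pure assumption. A claim that infections are lost chiefly in the IV group, or a count lost per 100 children, would go beyond the documents.

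Severity is minor. The issue concerns one component of a secondary safety outcome, mainly in comparison with a benchmark group of 100 that Section 1.4.3 says is not a formal control. The primary endpoint and sample size are unaffected. The conclusion rests on sites applying Table 9 as written, with no overriding instruction elsewhere.

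**What to change.** - In Section 9.2.2, delete the note that derives SAE status from a definition, and leave the SAE outcome to Table 9.
- In Sections 6.7 and 7.3.1.E, add that every hospital-acquired infection is recorded on the CRF whatever its grade, seriousness or relatedness.
- State an onset threshold for the term. The one in exclusion criterion 2 (more than 48 hours after admission) is available. Say also whether infections first noticed after discharge count; the week 1 contact already asks about intervening illness.
- List hospital-acquired infection as its own safety line in Section 9.2.2, reported by arm.

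The cost is one item on forms already completed daily in hospital and at week 1, a sentence in each section, and slightly more data entry at sites. Treatment, the primary analysis and the sample size do not change.
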